4.2 Follow-up and Daily Application of geko™ therapy (Days 1-9)

During daily review of the patient by a member of the healthcare team, a new geko™ device will be fitted bilaterally as per standard care. In addition, the following information will be collected each day or until the patient is able to mobilize independently:

- Length of time device worn for since fitting (hours)
- Adhesion to patient's leg (rate from very well to not at all)
- Use of additional fixation to keep the device in position
- Ease of re-application if removed
- Patient comfort (rate from very comfortable to extremely uncomfortable)
- Patient sleep post-fitting
- Patient's current mobility

Fit new geko™ device bilaterally for VTE prevention as per hospital standard care. Devices fitted will be as per allotted patient group and study phase and the following post-application information recorded:

- Ease with which device fitted (rate from very easy to impossible)

- Adhesion to patient's leg (rate from very well to not at all)
- Use of any additional fixation to keep the device in position.
- Patient comfort (rate from very comfortable to extremely uncomfortable)
- Device setting (1-11)
- Assess for any AEs

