7.4 Application of geko™ Device and Collection of Device Performance Data

Patients will receive treatment with either the geko™ T3 or XT-3 device as part of their standard care for VTE prevention as per hospital clinical protocol. During daily review of the patient by a member of the healthcare team, the following information will be collected for a maximum of 10 days or until the patient is able to mobilize independently:

- Length of time device worn for since fitting (hours)
- Adhesion to patient's leg (score from very well to not at all)
- Use of additional fixation to keep the device in position.
- Patient comfort
- Patient sleep post-fitting
- Patient's current mobility
- Ease with which device fitted (score from very easy to impossible)
- Device setting
- Assess for any AEs

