8.2 Sample Size Determination

The sample size of 20 patients per phase has been determined using MIL-STD-105, a standard commonly used in the medical device industry to specify sample size and provide the basis for acceptance and rejection. We set an acceptable quality level (AQL) of 0.15 for the function of the new formulation hydrogel and using the C=0 sampling plan (Table 2), 100% testing of 80 devices with no failures would confirm that we meet our specified AQL.

If completed on 20 patients and assuming 4 days of use (on both legs), this equates to a minimum of 80 XT-3 devices to test the new formulation the same numbers would be required for the T3 device with current hydrogel formulation for statistical comparison.

Table 2: MIL-STD-105 Statistical Sampling Plan (C=0 Sampling Plan)

MIL-STD-1916																	
Verification Level	VII		VI		V		IV		III		II		I				
INDEX VALUE																	
AQL	.010	.015	.025	.040	.065	.10	.15	.25	.40	.65	1.0	1.5	2.5	4.0	6.5	10	
LOT SIZE		SAMPLE SIZE															
2 TO 5	*	*	*	*	*	*	*	*	*	*	*	*	5	3	2	2	
9 TO 15	*	*	*	*	*	*	*	*	*	*	13	8	5	3	2	2	
16 TO 25	*	*	*	*	*	*	*	*	*	20	13	8	5	3	3	2	
26 TO 50	*	*	*	*	*	*	*	*	32	20	13	8	5	5	5	3	
51 TO 90	*	*	*	*	*	*	80	50	32	20	13	8	7	6	5	4	
91 TO 150	*	*	*	*	*	125	80	50	32	20	13	12	11	7	6	5	
151 TO 280	*	*	*	*	200	125	80	50	32	20	20	15	13	10	7	6	
281 TO 500	*	*	*	315	200	125	80	50	48	47	29	21	16	11	9	7	
501 TO 1,200	*	800	500	315	200	125	80	75	73	47	34	27	19	15	11	8	
1,201 TO 3,200	1250	800	500	315	200	125	120	116	73	53	42	35	23	18	13	9	
3,201 TO 10,000	1250	800	500	315	200	192	189	116	86	68	50	38	29	22	15	9	
10,001 TO 35,000	1250	800	500	315	300	294	189	135	108	77	60	46	35	29	15	9	
35,001 TO 150,000	1250	800	500	400	4776	294	218	170	123	96	74	56	40	29	15	9	
150,001 TO 500,000	1250	800	750	715	476	345	270	200	156	119	90	64	40	29	15	9	
500,001 AND OVER	1250	1200	1112	715	536	435	303	244	189	143	102	64	40	29	15	9	

* Indicates entire Lot must be inspected 100%. **Note:** Acceptance number in all cases is zero.

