8.4.2 Secondary Efficacy Endpoints

The secondary endpoints are:

- The incidence of adverse events (AEs), incidence of serious AEs (SAEs), incidence of study treatment related AEs, and the incidence of investigational device related AEs

Secondary endpoint data from this observational study will be summarised descriptively. Continuous parameters may include mean, standard deviation, median, minimum, and maximum.

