-------------------------------	-------------------------------	-------------------------------	-------------------------------	-------------------------------	-------------------------------	-------------------------------	-------------------------------	-------------------------------	--------------------------------	--------------------------------

CASE REPORT FORM	BASELINE (DAY 0)			DATE (DD/MM/YYYY)				
STUDY SITE:	THE ROYAL STOKE UNIVERSITY HOSPITAL							
PRINCIPAL INVESTIGATOR:	[name]							
SITE NUMBER	0	2	5	PATIENT NUMBER	0		PATIENT INITIALS	

Has the patient experienced any Adverse Events since signing the Informed Consent?

Yes No

If yes, please comment below:

CRF completed by:

Print Name: _____ Signature: _____ Date: ____/____/_____

To be completed by Principal Investigator:

I am confident that the information supplied in this case record form is complete and accurate data.

Signature: _____ Date: ____/____/_____

Follow-up Day 1 (please note days 1-9 CRFs will be the same)

CASE REPORT FORM		FOLLOW-UP 1 (DAY 1)			DATE (DD/MM/YYYY)	
STUDY SITE: PRINCIPAL INVESTIGATOR:		THE ROYAL STOKE UNIVERSITY HOSPITAL [name]				
SITE NUMBER		0  2  5 	PATIENT NUMBER	0   	PATIENT INITIALS	

How many hours did the patient wear the geko™ device for?					_____ hours
How well did the geko™ device stick to the patient's leg?					
Very Well Remained attached 	Well Detached in small area 	Poorly Detached over large area 	Very Poorly Detached completely 	Not at all Would not stick at all 	

If any level of detachment has been indicated, please provide a comment below:

Did the patient need any additional fixation to keep the geko™ device in position?				
None 	Micropore Tape 	Adhesive Accessory 	OnPulse™ Knee Strap 	

If removed was the geko™ device easily re-applied?				
Yes 	No 	N/A 		

If no, please comment below:

Overall, how comfortable was the geko™ device for the patient to wear?				

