Very Comfortable 	Comfortable 	Uncomfortable 	Very Uncomfortable 	Extremely Uncomfortable 

If any discomfort has been indicated, please provide a comment below:

Did the patient sleep with the device on?		Yes 	No 
---	--	------------------------------	-----------------------------

DAY 1: Application of geko™ device

Current mobility - Is patient able to walk independently? (If YES is selected patient CANNOT continue in the study - please complete EXIT form)				Yes 	No 
Study Phase	geko™ Device Fitted		Lot Number	Expiry Date	
Phase 1		geko™ T3			
Phase 2		geko™ X-T3			

CASE REPORT FORM	FOLLOW-UP 1 (DAY 1)			DATE (DD/MM/YYYY)	/	/
STUDY SITE: THE ROYAL STOKE UNIVERSITY HOSPITAL	PRINCIPAL INVESTIGATOR: [name]					

SITE NUMBER

0	2	5
---	---	---

 PATIENT NUMBER

0		
---	--	--

 PATIENT INITIALS

--	--

How easy was it to apply the geko™ device to the patients leg?

Very Easy 	Easy 	Difficult 	Very Difficult 	Impossible 
---------------------------------------	----------------------------------	---------------------------------------	--	--

If there were any difficulties, please provide a comment below:

Once applied, how comfortable for the patient was the geko™ device?

Very Comfortable 	Comfortable 	Uncomfortable 	Very Uncomfortable 	Extremely Uncomfortable 
--	---	---	--	---

If any discomfort has been indicated, please provide a comment below:

Which setting was the geko™ device set to?

1 	2 	3 	4 	5 	6 	7 	8 	9 	10 	11 

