-------------------------------	-------------------------------	-------------------------------	-------------------------------	-------------------------------	-------------------------------	-------------------------------	-------------------------------	-------------------------------	--------------------------------	--------------------------------

Has the patient experienced any Adverse Events since signing the Informed Consent?

Yes No

If yes, please comment below:

CRF completed by:

Print Name: _____ Signature: _____ Date: ____/____/_____

To be completed by Principal Investigator:

I am confident that the information supplied in this case record form is complete and accurate data.

Signature: _____ Date: ____/____/_____

Final Follow-up Day 10

CASE REPORT FORM	FINAL FOLLOW-UP 10 (DAY 10)			DATE (DD/MM/YYYY)	_____/_____/_____					
STUDY SITE: PRINCIPAL INVESTIGATOR:	THE ROYAL STOKE UNIVERSITY HOSPITAL [name]									
SITE NUMBER	0	2	5	PATIENT NUMBER	0			PATIENT INITIALS		

How many hours did the patient wear the geko™ device for?					_____ hours
How well did the geko™ device stick to the patient's leg?					
Very Well Remained attached 	Well Detached in small area 	Poorly Detached over large area 	Very Poorly Detached completely 	Not at all Would not stick at all 	

If any level of detachment has been indicated, please provide a comment below:

Did the patient need any additional fixation to keep the geko™ device in position?				
None 	Micropore Tape 	Adhesive Accessory 	OnPulse™ Knee Strap 	

If removed was the geko™ device easily re-applied?				
Yes 	No 	N/A 		

If no, please comment below:

Overall, how comfortable was the geko™ device for the patient to wear?				
Very Comfortable 	Comfortable 	Uncomfortable 	Very Uncomfortable 	Extremely Uncomfortable 

If any discomfort has been indicated, please provide a comment below:

Did the patient sleep with the device on?	Yes 	No 
---	------------------------------	-----------------------------

Any other comments – please add below

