Day 10 final assessment and patient participation completed. Please complete Exit CRF

CASE REPORT FORM	FINAL FOLLOW-UP 10 (DAY 10)		DATE (DD/MM/YYYY)	____ / ____ / _____
STUDY SITE: PRINCIPAL INVESTIGATOR:	THE ROYAL STOKE UNIVERSITY HOSPITAL [name]			

SITE NUMBER

0	2	5
---	---	---

 PATIENT NUMBER

0		
---	--	--

 PATIENT INITIALS

--	--

CRF completed by:

Print Name: _____ Signature: _____ Date: ____ / ____ / _____

To be completed by Principal Investigator:

I am confident that the information supplied in this case record form is complete and accurate data.

Signature: _____ Date: ____ / ____ / _____

Exit Day 10

CASE REPORT FORM	EXIT			DATE (DD/MM/YYYY)	____ / ____ / ____					
STUDY SITE:	THE ROYAL STOKE UNIVERSITY HOSPITAL									
PRINCIPAL INVESTIGATOR:	[name]									
SITE NUMBER	0	2	5	PATIENT NUMBER	0			PATIENT INITIALS		
Study Exit Date (DD/MM/YYYY)	____ / ____ / ____									
Date of Last Assessment (DD/MM/YYYY)	____ / ____ / ____									
Last Assessment Completed	Baseline  Follow-up 1  Follow-up 2  Follow-up 3  Follow-up 4  Follow-up 5  Follow-up 6  Follow-up 7  Follow-up 8  Follow-up 9  Follow-up 10 									
Reason for Exit from Study	Study completed  Lost to follow-up  Non-compliance  Medical contraindication  Consent withdrawn  Other** 									
**Additional explanation required:										

CRF completed by:

Print Name: _____ Signature: _____ Date: ____ / ____ / ____

[figure not shown]
To be completed by Principal Investigator:

I am confident that the information supplied in this case record form is complete and accurate data.

[figure not shown]
Signature: _____ Date: ____ / ____ / ____

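### On the Day 1–9 form the exit instruction comes before the adverse-event question, and the Exit form has none, so a patient who leaves on regaining mobility may have no solicited AE record for the last wear interval

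*Combined protocol and SAP*

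**What the plan says.** Appendix 3 gives one daily follow-up form and notes: "please note days 1-9 CRFs will be the same". Its items run in this order:

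1. Review of the device just worn: hours, adhesion, extra fixation, re-application, comfort, sleep.
2. The application block, which opens with the mobility item and the instruction "If YES is selected patient CANNOT continue in the study - please complete EXIT form".
3. On the next page, ease of fitting, comfort and setting of the new device.
4. The question "Has the patient experienced any Adverse Events since signing the Informed Consent", followed by the signatures of the person completing the form and the principal investigator.

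The Exit form records dates, the last assessment completed and the "Reason for Exit from Study". It does not ask about AEs.

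Section 4.2 has the same order. The AE check is the last item of the list introduced by "Devices fitted will be as per allotted patient group and study phase and the following post-application information recorded", and Section 4.0 says that the listed order is to be followed. Section 7.4 has the daily data, AEs included, "collected for a maximum of 10 days or until the patient is able to mobilize independently". Table 1 marks AE assessment at baseline and in the Days 1–10 column.

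The secondary endpoints in Section 8.4.2 are all AE measures: "The incidence of adverse events (AEs), incidence of serious AEs (SAEs), incidence of study treatment related AEs, and the incidence of investigational device related AEs".

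**The concern.** On the day a patient is found able to walk, staff rate the adhesion of the last device and then meet an instruction that sends them to another form. The AE question lies beyond that instruction, behind items that do not apply to this patient. If they stop there, the last wear interval counts towards the primary endpoint but has no solicited safety record. Because the AE question looks back to consent, a missed prompt on an ordinary day is recovered at the next review. On the exit day there is no next review.

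Section 1.3 gives lower skin irritation as part of the case for the new gel, and the instructions for use list skin irritation as a side effect. A mild skin reaction is the sort of event that tends to be recorded only if someone asks. The cohorts are sequential and not randomised, so if they regain mobility at different speeds, the unprompted share could differ between them.

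**Working it through.** **The plan's own figure.** Section 8.2 is the only place with a duration of use: 20 patients per phase, "assuming 4 days of use (on both legs"), said to give a minimum of 80 devices. As written, 20 × 4 × 2 = 160. The figure of 80 needs one leg for 4 days (20 × 4 × 1) or both legs for 2 days (20 × 2 × 2). The 4 days is thus a planning assumption that does not agree with its own total. It serves below only as an illustration.

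**Unprompted share.** A patient fitted on Day 0 who exits on Day k has worn devices over k intervals. If the Day k form is stopped at the mobility item, the last AE prompt was on Day k − 1, so k − 1 intervals are covered and the unprompted share is 1/k.

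- Day 1: 1/1 = 100%. The only AE prompt was at the Day 0 fitting.
- Day 2: 1/2 = 50%.
- Day 4: 1/4 = 25%.
- Day 9: 1/9 = 11%.

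If the rest of the form is completed, the share is 0.

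**Day 10 completers.** Neither Section 4.3 nor the Day 10 form has an AE item, although Table 1 covers Day 10. Their unprompted share is 1/10 = 10%, and it does not depend on how staff read an exit instruction.

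**What this could mean for incidence.** The plan states no AE rate, so the AE risk per wear interval, p, is an assumption. With constant p, the chance of at least one AE is 1 − (1 − p)^k, and the chance of one in a prompted interval is 1 − (1 − p)^(k−1). For exit on Day 4:

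| Assumed p | All 4 intervals | First 3 intervals | Relative shortfall | Patients of 20 |
|---|---|---|---|---|
| 0.01 | 0.0394 | 0.0297 | 24.6% | 0.19 |
| 0.03 | 0.1147 | 0.0873 | 23.9% | 0.55 |
| 0.05 | 0.1855 | 0.1426 | 23.1% | 0.86 |
| 0.10 | 0.3439 | 0.2710 | 21.2% | 1.46 |

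The last column is 20 × p(1 − p)^3. The table is an upper case for Day 4: it takes all 20 patients to leave that day by walking, every form to be stopped at the instruction, and no AE from the last interval to reach the record by another route. For Day 10 completers over the same range of p, the relative shortfall is 9.6% down to 5.9%, or 0.18 to 0.77 patients of 20.

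**The case against.** The strongest reply is that no skip is written. The form tells staff to complete the Exit form; it does not tell them to leave the second page blank. The Day k signatures sit directly below the AE question, the principal investigator certifies the form as complete, and monitors check forms against completion guidelines that are not in the document. Table 1 supports asking on the exit day. This stands, and a reader who infers that the last interval is bound to be lost goes further than the documents do. It does not remove the risk: the items in between are about a device this patient does not get, and the Exit form has its own signature block at which the record can be closed.

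Three other strong readings also fail.

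- *That every AE endpoint is affected.* Section 9.1 requires device-related AEs to go to the sponsor within 24 hours and SAEs to be reported under local law. Section 5.2 sends discontinuations due to an AE to Section 9.0. The comfort item, with free text, comes before the exit instruction and may pick up some skin symptoms, though it is not an AE record. The exposed part is mainly non-serious AEs not reported as device-related. Against that, Section 9.1 relies on the physician becoming aware of the event, and the plan does not say that these reports feed the incidence counts.
- *That the typical patient under Section 8.2 loses a quarter of the record.* Section 8.2 uses 4 days to reach a device count. It does not say that patients leave then, or leave because they walk, and Section 3.1 describes patients confined to bed.
- *That Section 7.4 itself drops AEs on the exit day.* Its clause governs adhesion and AEs alike, so it creates no difference between them. The difference comes from the form layout and the order in Section 4.2.

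A marked distortion between cohorts is likewise not shown. With assumed exits on Day 3 and Day 6 and p = 0.03, the incidences over all intervals are 8.7% and 16.7% (ratio 1.9) and over prompted intervals 5.9% and 14.1% (ratio 2.4). Most of that contrast is unequal exposure, and both exit days are invented. The endpoints are also descriptive, with no test or decision rule.

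**Conclusion.** The point holds as a weakness in data capture. The order of items, the exit instruction ahead of the AE question and the absence of an AE item on the Exit form can all be read from Appendix 3. Section 4.2 repeats the order, and it sits poorly with Table 1. An early leaver may have the last device rated for adhesion with no solicited AE record for the same interval.

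The size is conditional. If staff stop at the instruction, the unprompted share is 1/k for exit on Day k; if they finish the form, it is nil. The plan gives neither a mobilisation rate nor an AE rate, so no figure for the effect on incidence can be fixed, and the table above is only an illustration under assumed risks. The direction is known: recorded incidence of the exposed events can only be too low. As AE incidences are the whole of the secondary endpoints and the remedy is nearly free, the change is worth making.

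**What to change.** 1. On the Day 1–9 form, move the AE question into the review of the worn device, ahead of the mobility item and its exit instruction.
2. In Sections 4.2 and 7.4, state that AEs are assessed at the review on the day of exit, including when the patient is found able to walk.
3. On the Exit form, add a line asking for any AE since the last completed review. This covers patients who leave by other routes, and Day 10 completers, whose form has no AE item.

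One further sentence saying whether Section 9.1 reports count towards the incidence endpoints would settle the remaining doubt.

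The cost is one item moved, one line added and a sentence in each of two sections, with no extra visit, staff or patients. The small downside is that recorded AE incidence may rise slightly.

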2.1.2 Secondary Efficacy Endpoints

- The secondary endpoints are the incidence of adverse events (AEs), incidence of serious AEs (SAEs), incidence of study treatment related AEs, and the incidence of investigational device related AEs

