4.3 Final Follow-up and End of Participation (Day 10)

At the final follow-up, the following information will be collected

- Length of time device worn for since fitting (hours)
- Adhesion to patient's leg (rate from very well to not at all)
- Use of additional fixation to keep the device in position
- Ease of re-application if removed
- Patient comfort (rate from very comfortable to extremely uncomfortable)
- Patient sleep post-fitting
- Patient's current mobility

Once the final follow-up has been completed the patient's participation will end and the patient will be exited from the study.

See Table 1 for full schedule of events.

Procedure / Assessment	Baseline (Day 0)	Follow-up (Days 1-10)
Confirmation of eligibility	X	
Informed Consent	X	
Demographics (age in years, date of birth, gender, date of stroke diagnosis, mobility, adjunctive treatments to the geko™ device e.g. drugs, stockings	X	
Bilateral fitting of geko™ devices as per standard care	X	X
Ease of fitting	X	X
Adhesion to patient's leg	X	X
Additional fixation	X	X
Ease of re-application if device removed	X	X
Patient comfort post fitting	X	X
Device setting	X	X
Patient sleep post-fitting	X	X
Hours of wear since fitting	X	X
Patient mobility	X	X
Assess for AEs	X	X

Table 1: Schedule of Events.

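### Table 1 schedules adverse event assessment to Day 10 but Section 4.3 and the Day 10 and Exit forms omit it, and no form shown has the seriousness or relatedness fields that three of four secondary endpoints need

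*Combined protocol and SAP*

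**What the plan says.** Section 2.1.2 sets four secondary endpoints: the incidence of AEs, and the "incidence of serious AEs (SAEs), incidence of study treatment related AEs, and the incidence of investigational device related AEs". Section 8.4.2 repeats them.

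**Timing.** Sections 4.1 (Day 0) and 4.2 (Days 1-9) both list an AE assessment. Table 1 has one follow-up column, "Follow-up (Days 1-10", and marks the row "Assess for AEs" in it. Section 7.4 includes "Assess for any AEs" in the daily review, with information "collected for a maximum of 10 days or until the patient is able to mobilize independently". Section 4.3 opens the Day 10 visit with "At the final follow-up, the following information will be collected" and lists seven items: hours worn, adhesion, extra fixation, re-application, comfort, sleep and mobility. AEs are not among them, and participation ends after that visit.

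**Forms.** Appendix 3 is headed as sample case report forms (CRFs), though Section 10.0 says that it holds all of the study's CRFs. On the Baseline and Days 1-9 forms the AE item is one cumulative Yes/No question, "Has the patient experienced any Adverse Events since signing the Informed Consent", with a comment box. On the Days 1-9 form it is the last data item. It stands well after a mobility question that sends staff to the Exit form if the patient walks independently. The Day 10 and Exit forms have no AE question.

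**Safety reports.** Section 9.1 asks the treating physician to report device-related AEs to the sponsor within 24 hours, and ties SAE reporting to local law.

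**The concern.** An incidence endpoint depends on the prompts and fields that feed it. Two things look wrong here.

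First, the schedule and the forms disagree on whether AEs are assessed at the last contact. Because the question covers everything since consent, an event missed on one day can be picked up on the next. An event in the final interval before exit cannot.

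Second, the plan promises SAE, treatment-related and device-related incidence, but a Yes/No with free text records neither seriousness nor relatedness. Someone would have to assign these afterwards, with no stated rule, in a non-blinded comparison of two sequential groups.

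Safety is not incidental in this study. Section 1.3 gives lower skin irritation as a promised advantage of KM40C, Appendix 4 names irritation as a side effect, and no CRF shown has a skin item. Irritation would reach the data through the AE question, the comfort items or the comments.

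**Working it through.** The plan gives no figure of its own on this point, so the check is a comparison of texts followed by counts.

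**Inputs.** 20 patients per group (Section 3.2). Devices fitted on Day 0 and on each of Days 1-9, each reviewed the next day, with the last review on Day 10 (Sections 4.1 to 4.3). Section 8.2's "assuming 4 days of use (on both legs", used here only as an example of a patient who exits at Day 4 (an assumption). The forms in Appendix 3.

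**Step 1: where an AE assessment appears.**

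| Source | Day 0 | Days 1-9 | Day 10 | Exit |
|---|---|---|---|---|
| Section 4 lists | yes | yes | no | not listed |
| Table 1 | yes | yes | yes | not listed |
| CRFs | yes | yes | no | no |

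**Step 2: 10-day completers.**
- AE prompts per patient: Table 1 gives 1 + 10 = 11; the CRFs give 1 + 9 = 10.
- Wear intervals per patient, Day 0-1 to Day 9-10: 10. Followed by an AE prompt: 9. Unprompted: 1 of 10.
- Per group, if all complete: 20 × 10 = 200 patient-intervals, of which 20 × 1 = 20 are unprompted; 20/200 = 10%.

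**Step 3: mobility exits on Days 1-9.** A patient leaving at Day d has d wear intervals. On that day's form the order is: items on the device just worn, mobility question with the exit instruction, items on fitting the next device, AE question.
- If staff stop at the instruction, 1 of d intervals is unprompted. At d = 4 this is 1/4 = 25%; at d = 9 it is 1/9 = 11%.
- If staff finish the form, 0 of d is unprompted.
- Illustration for a group: if all 20 left for mobility at Day 4, there would be 20 × 4 = 80 patient-intervals, with 20/80 = 25% or 0/80 = 0% unprompted.

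By these two routes a patient loses at most one interval, the final one. The percentage depends on how long patients stay and on how staff read the form.

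**Step 4: fields for the secondary endpoints.** Forms shown: Baseline 1 + Days 1-9 9 + Day 10 1 + Exit 1 = 12. With an AE question: 1 + 9 = 10. With a field for seriousness, relation to treatment or relation to device: 0. The Yes/No supports the number of patients with any AE. The other three of the four endpoints have no structured field. The cumulative question also gives no event counts or onset dates.

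**The case against.** **Table 1 is coarse.** Its Days 1-10 column also marks fitting, ease of fitting and device setting, which Day 10 does not collect. At baseline it marks hours of wear and sleep, which Section 4.1 does not list. A mark in it is therefore weak evidence of what is due on a given day. Section 7.4 is weaker still, because its 10-day limit could mean Days 0-9. A reader might infer that two places firmly require an AE assessment on Day 10; the documents do not support that strength. What stands is that Table 1 and Section 4.3 disagree, and that nothing explains leaving AEs off the last day.

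**Other routes exist.** A reader might infer that Day 10 events, or SAEs in general, would be lost. The documents do not support that either. The Day 10 form has a comfort item and a general comment box. The Exit form has options for medical contraindication and other reasons. Section 11.2 has monitors verify CRFs against source documents, Section 13.3 has the site keep SAE reports, and a Section 9.1 report identifies an event as device-related by its own trigger. CRF completion guidelines and a Data Management Plan (Section 13.2) may add rules, but they are not among the documents. What stands is that no text carries these reports into the endpoint data, and a late non-serious event not judged device-related has no assured route.

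**Sample forms.** The heading of Appendix 3 leaves room for further forms, while Section 10.0 says that all are there. The claim is therefore limited to the CRFs shown.

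**Section 8.4.2.** A reader might infer from its list of continuous summaries that incidences will be reported as means. The wording is permissive and does not say so. The only gap is that the unit, patient or event, is not stated.

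**Conclusion.** Both parts hold. The schedule and the Day 10 materials disagree on AE assessment, and three of the four secondary endpoints lack a structured field on any of the 12 forms shown. The missing fields are the larger problem, because they affect every patient on every form.

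The Day 10 gap is up to 20 of 200 patient-intervals per group if all patients complete. A reader might take that 10% as a ceiling, but it is not one: with mobility exits the share can be higher (25% in the Day 4 example) or zero, depending on whether staff stop at the exit instruction, which the documents do not settle. Nor can the documents support a ceiling on how far any-AE incidence would be understated, since they give no AE rate per interval.

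The same forms serve both groups, so the gap does not by itself favour either device. The primary analysis is unaffected: adhesion is recorded on the Day 10 form and, on the Days 1-9 form, before the exit instruction. The sample size does not rest on AEs. The change should be made, but it concerns the secondary endpoints only.

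**What to change.** 1. Add the AE item to Section 4.3 and the Day 10 CRF, and reconcile Table 1 with Section 4.3 as a whole, including the rows on fitting, ease of fitting and device setting. The sponsor must state what Day 10 is meant to include.
2. On the Days 1-9 form, place the AE question before the mobility question and its exit instruction.
3. Keep the Yes/No question as the trigger and add an AE log with one line per event: description, onset date, serious Y/N, related to treatment Y/N, related to device Y/N. Reconcile the log with the Section 9.1 reports.
4. In Section 8.4.2, report for each endpoint the number and proportion of patients per group with at least one such event.

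A completer would then have 11 of the 11 prompts in Table 1 and a prompt after 10 of 10 wear intervals, and 4 of 4 secondary endpoints would have a structured field.

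The cost is a CRF revision, a protocol amendment with ethics approval (Sections 11.3 and 12.1) and a little investigator time per event. No extra visits or patients are needed.
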